9.4.5 MCM Monitoring and Signal Generation

On an ongoing basis, the registry teratologist and SAC will review all reports of MCM individually and cumulatively for potential signals that are generated in the collection of this information. The registry will adopt a plan developed by the Antiretroviral Pregnancy Registry to determine what constitutes a signal for a MCM, how it is reviewed, and what action might be taken should such a signal be seen (Covington, 2004). For example, the “Rule of Three” convention specifies that once 3 similar MCMs have accumulated with any specific exposure, these cases are flagged for immediate review. The likelihood of finding 3 of any specific MCM in a cohort of <600 by chance alone is less than 5% for all but the most common MCM classes (i.e., those occurring with the rate of <1/700). To enhance the insurance of prompt, responsible, and appropriate action in the event of a potential signal, the registry will employ the strategy of “threshold” based on the Council of International Organizations for the Medical Sciences (CIOMS, 1999). The threshold for action will be determined by the extent of certainty about the cases and tempered by the specifics of the cases.

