9.5 Study Size

The pregnancy registry is a PMC agreed upon with the CBER to commence enrolment on 31 January 2016 and to continue for a period of 3 years or pending CBER review and discussion of results with GSK. will submit a full study report to CBER by 31 May 2020.

The registry will prospectively enroll women with confirmed or possible (i.e. if the brand is unknown) exposure to BEXSERO 30 days prior to LMP or at any time during pregnancy. BEXSERO is not contraindicated during pregnancy, but should be used during pregnancy only if clearly needed. Under the current ACIP recommendations, the CDC estimates 350,000 individuals will be advised to receive a meningococcal B vaccine (MacNeil, 2015), of whom it is likely that a small proportion will be exposed during pregnancy. There are uncertainties regarding the degree of market penetration and vaccine uptake that will be achieved in at-risk groups. A recent US study of the safety of Cervarix[®] in pregnancy was terminated due to low accrual of subjects attributed to low uptake of the vaccine in the US (GSK, 2015). To account for this, and that the proportion of clinically recognized pregnancies that can be expected to result in a live birth is approximately 62% (Martin, 2015), a range of sample size estimates was considered, from a minimum of 5 to 150 live births.

It is likely that the majority of exposures (99%) will be the result of inadvertent exposure within 30 days prior to LMP or early in the first trimester before pregnancy status is known. If exposures occur later in pregnancy, results will be stratified by trimester of exposure, acknowledging that the power of stratified analyses to detect statistically significant differences will be limited by the sample size of each subgroup.

The expected low frequency of BEXSERO exposure in pregnancy will limit the statistical power of this study. As the sample size of the study increases, there will be a corresponding increase in the power of the study to detect increases in the prevalence of outcomes. The study will have greater power to detect prevalence increases for relatively common outcomes (with higher prevalence) but will have less power to for more uncommon outcomes, such as MCM.

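### Does Section 9.4.5 attach its 5% chance bound for the Rule of Three to the wrong malformation classes?

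*Combined protocol and SAP*

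**What the plan says.** Section 9.4.5 takes over a signal plan from another pregnancy registry. Its one numeric rule is that "once 3 similar MCMs have accumulated with any specific exposure, these cases are flagged for immediate review". The next sentence gives the reason for choosing three. For a cohort below 600 births, it puts the probability that three cases of one malformation arise purely by chance at "less than 5% for all but the most common MCM classes (i.e., those occurring with the rate of <1/700"). No formula or calculation is shown.

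The same section says that the registry teratologist and the Scientific Advisory Committee "will review all reports of MCM individually and cumulatively for potential signals". It makes the threshold for action depend on how certain the cases are and on their particulars. On registry size, Section 9.5 says that "a range of sample size estimates was considered, from a minimum of 5 to 150 live births".

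**The concern.** Two things look wrong.

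- **Direction of the inequality.** A bracket opening with i.e. normally explains the phrase just before it, which here is the commonest classes. A rate below 1/700 describes rarer classes. Read that way, the sentence exempts rare malformations and gives the 5% assurance to common ones, where three chance cases are most likely.
- **Size of the bound.** Suppose the bracket is meant to describe the covered classes. A flag is still raised once three cases have accumulated, so the relevant event is three or more. At 1/700 and almost 600 births that probability is slightly above 5%.

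This sentence is the only error property that Section 9.4.5 states for its only numeric rule. If someone used it to judge a flag, they could trust a cluster of a common defect too readily and discount a cluster of a rare one.

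**Working it through.** **Inputs.** All come from the protocol: trigger of three cases, cohort below 600 (largest value 599), bound 5% and cut-off 1/700 (Section 9.4.5); registry size 5 to 150 live births (Section 9.5). Probabilities are exact binomial and apply to one malformation class at a time.

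**Reproducing the plan's figure** at n = 599, p = 1/700:

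- P(0) = (699/700)^599 = 0.4247
- P(1) = P(0) × 599/699 = 0.3640
- P(2) = P(1) × 598/(2 × 699) = 0.1557
- P(3) = P(2) × 597/(3 × 699) = 0.0443
- P(3 or more) = 1 − (0.4247 + 0.3640 + 0.1557) = 0.0556

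Exactly three gives 4.43%, under the stated bound. Three or more gives 5.56%, over it by 0.56 points.

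**Across class rates:**

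| Class rate | P(3 or more), n = 599 | P(exactly 3), n = 599 | P(3 or more), n = 150 |
|---|---|---|---|
| 1/300 | 32.2% | 18.0% | 1.42% |
| 1/500 | 12.0% | 8.6% | 0.35% |
| 1/600 | 8.0% | 6.1% | 0.21% |
| 1/700 | 5.56% | 4.43% | 0.14% |
| 1/735 | 4.95% | 3.99% | 0.12% |
| 1/1000 | 2.3% | 2.0% | 0.05% |
| 1/2000 | 0.36% | 0.33% | below 0.01% |

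**Reading 1: the bracket defines the commonest classes.** The bound would then cover rates of 1/700 and above. At n = 599 it fails for three or more throughout that range in the table. Counting exactly three does not rescue it at 1/600, 1/500 or 1/300. The classes it would exempt, such as 1/1000 and 1/2000, are the ones where it holds. On this reading the sign is reversed.

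**Reading 2: the bracket defines the covered classes.** The sign is right. For exactly three the bound holds, because at n = 599 that probability reaches 5% only at about 1/661. For three or more it reaches 5% at about 1/732 when n = 599. At 1/700 it passes 5% between n = 572 (4.98%) and n = 573 (5.0005%). The shortfall is therefore confined to rates between about 1/732 and 1/700 in cohorts of 573 to 599.

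**At the sizes in Section 9.5.** With 150 live births, three or more has a probability of 0.14% at 1/700. It reaches 5% only at about 1/183. Even the commoner classes that reading 1 brings under the bound (1/600, 1/500, 1/300) stay at 1.42% or less.

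**What uses the 1/700 figure.** The flag is raised at three similar cases for every class. The threshold for action depends on case certainty and particulars. The prevalence estimates and confidence intervals in Section 9.7.3 do not refer to 1/700. Changing the symbol would alter none of these.

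**The case for a change.** The best case for a change is that the sentence is correct only if two favourable choices are made together: the less natural parse of the bracket, and exactly three in place of three or more. The second choice is the wrong quantity for a flag, because a fourth similar case does not withdraw it. The registry adopts the rule as its own, so borrowing it does not excuse the wording, and a repair would cost one symbol.

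Much of this stands. The bracket is reversed on its ordinary reading and at best ambiguous, and three or more is the event that raises a flag. What does not stand is any consequence. The sentence explains why three was chosen; it does not set the rule. Its round figures (600, 5%, 1/700) read as background to an adopted convention, and no error rate or decision is tied to them. The sense is also easy to recover, since chance clusters are plainly more likely for common defects. Resetting the cut-off to a more exact value such as 1/735 would also go too far: the excess at 1/700 arises only from 573 births upward, and the basis of the adopted figure cannot be seen in the protocol.

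**Conclusion.** The wording is faulty, but the fault is clerical and correcting it gains nothing in the conduct or analysis of the registry. On the ordinary reading the inequality is reversed. On the other reading the 5% bound is exact enough for its purpose: 4.43% for exactly three, and at most about 5.56% for three or more at the very edge of the stated range. Neither reading affects when a flag is raised, who reviews it or what is estimated. At the 5 to 150 live births considered, the chance of three or more at 1/700 is at most 0.14%, so a statistician or committee member using the sentence in either sense would not be misled about a flag in a class rarer than about 1/183.

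This rests on three assumptions: independent cases with a constant class rate; probabilities per single class, as the protocol states them, and not across all classes together; and a registry no larger than Section 9.5 considers. A cohort approaching 600 would make the direction of the inequality worth attention when a flag is interpreted, but the rule itself would still work the same way.

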9.5 Study Size

The pregnancy registry is a PMC agreed upon with the CBER to commence enrolment on 31 January 2016 and to continue for a period of 3 years or pending CBER review and discussion of results with GSK. will submit a full study report to CBER by 31 May 2020.

The registry will prospectively enroll women with confirmed or possible (i.e. if the brand is unknown) exposure to BEXSERO 30 days prior to LMP or at any time during pregnancy. BEXSERO is not contraindicated during pregnancy, but should be used during pregnancy only if clearly needed. Under the current ACIP recommendations, the CDC estimates 350,000 individuals will be advised to receive a meningococcal B vaccine (MacNeil, 2015), of whom it is likely that a small proportion will be exposed during pregnancy. There are uncertainties regarding the degree of market penetration and vaccine uptake that will be achieved in at-risk groups. A recent US study of the safety of Cervarix[®] in pregnancy was terminated due to low accrual of subjects attributed to low uptake of the vaccine in the US (GSK, 2015). To account for this, and that the proportion of clinically recognized pregnancies that can be expected to result in a live birth is approximately 62% (Martin, 2015), a range of sample size estimates was considered, from a minimum of 5 to 150 live births.

It is likely that the majority of exposures (99%) will be the result of inadvertent exposure within 30 days prior to LMP or early in the first trimester before pregnancy status is known. If exposures occur later in pregnancy, results will be stratified by trimester of exposure, acknowledging that the power of stratified analyses to detect statistically significant differences will be limited by the sample size of each subgroup.

The expected low frequency of BEXSERO exposure in pregnancy will limit the statistical power of this study. As the sample size of the study increases, there will be a corresponding increase in the power of the study to detect increases in the prevalence of outcomes. The study will have greater power to detect prevalence increases for relatively common outcomes (with higher prevalence) but will have less power to for more uncommon outcomes, such as MCM.

According to the CDC MACDP, the prevalence of MCMs for mothers <25 years of age in the US is 2.54% (Correa, 2007). According to the CDC National Vital Statistics System (NVSS), the prevalence of preterm birth and LBW for mothers <25 years of age are 11.71% and 8.50%, respectively (Martin, 2015).

The table below depicts sample sizes of 5, 20, 50, 100, and 150 live births and the associated effect sizes (i.e., the ratio of the registry-derived prevalence versus the reference prevalence) that would be detectable using a binomial distribution, a power of 80%, and a 1-sided Type I (false positive) error rate of 5% (Altman, 1991). For example, with a sample size of 100 live births, the study will have 80% power to detect a 1.79-fold

increase in the prevalence of preterm birth compared with the reference of 11.71% (population prevalence). In other words, if the registry-derived prevalence estimate is at least 1.79 times higher than the reference prevalence of preterm birth, the 1-sided 95% confidence interval for the estimate will exclude 11.71% (i.e., will lie above 11.71%), with a probability of 80%.

Table 9.5-1 Detectable effect size assuming 80% power

Sample size (N of live births)	Effect size (ratio of the registry-derived prevalence versus the reference prevalence for mothers <25 years of age)		
	MCM [reference = 2.54%]	PTB [reference = 11.71%]	LBW [reference = 8.50%]
5	19.30	5.75	7.92
20	7.95	3.13	3.69
50	4.23	2.24	2.59
100	3.07	1.79	1.96
150	2.66	1.63	1.82

Abbreviations: LBW = low birth weight; MCM = major congenital malformations; PTB = preterm birth.

9.6 Data Management

9.6.1 Data Processing

Data for this prospective registry will be managed with an electronic data capture (EDC) platform, which is 21 Code of Federal Regulations (CFR) Part 11 compliant. Participants and their HCPs will provide data over the phone or by completing a paper case report form (CRF), which can be submitted to the registry via mail or fax. The data will be reviewed by a registry clinical research associate for correctness and completeness and entered into the database.

9.6.2 Software and Hardware

Power calculations presented in this protocol were conducted using SAS statistical software and a 1-sample binomial distribution with a 1-sided Type I error rate of 5%. Data analyses will be performed similarly using SAS (version 9.2 or higher; SAS Institute, Cary, NC).

9.7 Data Analysis

Registry Case Management and Disposition

Prospective Registry Reports

The registry will encourage prospective registration, which is defined as registration of a pregnancy exposure prior to knowledge or perceived knowledge of the pregnancy outcome (e.g., structural defect or genetic abnormality noted on a prenatal test). Those with no abnormalities identified on a prenatal test prior to enrollment will be considered prospective and included in the analysis. The rationale, potential bias, and analytic techniques to address any bias that may be introduced by this practice are addressed in [Section 9.7.4](#).

Data from HCP networks and HMOs that provide de-identified data on all exposed pregnancies in their network will fall into the category of prospective registry reports, as these networks/HMOs provide objective data on every pregnancy exposure in the network/HMO, both positive and negative outcomes. Thus, they avoid the reporting bias inherent in retrospective reporting only after a negative outcome has been noted.

Retrospective Registry Reports

Retrospective reports will also include subjects for whom the pregnancy outcome has already occurred or an abnormality has been identified on a diagnostic or screening prenatal test prior to enrollment. Retrospective reports can be biased toward the reporting of more unusual and severe cases and are less likely to be representative of the general population experience than reports reported prior to knowledge of outcome. Therefore, retrospective reports will not be included in the primary analysis and statistical calculations. Retrospective reports with reported MCMs and/or spontaneous fetal losses will be reviewed to aid in detection of early signals and listed in registry reports. Retrospective reports will not be actively solicited by the registry and will not be captured in the registry database unless a congenital anomaly is reported.

Loss to Follow-up

For a prospective report or pregnancy where follow-up information on the pregnancy outcome (live birth, fetal loss, etc.) is never obtained or is unavailable, the pregnancy will be considered lost to follow-up. Subjects lost prior to pregnancy outcome will be tallied in the registry reports but not included in the statistical analyses.

Duplicate Registry Reports

With registry reports coming from multiple HCPs, HCP networks, and HMOs, it is important to ensure that each case is counted only once ([NBDPN, 2004](#)). Identification of duplicate reports may be problematic for the anonymously reported de-identified cases where there is no specific identifying information. Reports received by the registry will be reviewed for possible duplicate reporting. On receipt of a registration form, the report will

be compared with other reports made by the same reporter or compared with other data (such as age, LMP, EDD, and exposure information) to determine if the same report was received previously. If no duplication is identified, the report will be entered into the database. If a duplicate report is later identified through recall or the systematic check for duplicates, the case reported earliest or the one with the most complete data will be maintained as the valid case and updated with any data from the other report not already captured. The duplicate report will be flagged and designated as “Invalid,” with the reason being noted as “duplicate report.”

Evaluable Registry Reports

An evaluable report is a subject with data submitted or confirmed by an HCP that contains at least the minimum criteria for a report and is not lost to follow-up. Prospectively reported evaluable subjects with known outcomes will be included in the primary analysis for the registry report. Evaluable retrospective reports will be summarized separately in the report. Patient-reported data without HCP confirmation will be summarized separately in the report.

Invalid Registry Reports

An invalid registry report is a report for which the minimum data elements are never obtained despite requests for the missing data. If the minimum data are not provided initially, the report will be considered to be pending until all attempts to resolve queries for missing data and requests for follow-up information are complete. If, after all attempts at follow-up are made, the minimum criteria are still not met, the report will be considered invalid due to insufficient information. Invalid reports will not be included in the registry analyses.

Analysis Population

The primary population for analysis will include prospective evaluable participants exposed to BEXSERO that are not lost to follow-up (i.e., participants with appropriate outcome information that meet the minimum criteria for evaluation). Because early prenatal testing is so frequent, it may be difficult to achieve adequate numbers of prospectively identified pregnant women if all pregnancies with prior prenatal testing are excluded from the analysis. Therefore, the primary analysis will include pregnancies enrolled prior to outcome but after prenatal testing as long as the test does not indicate the presence of an abnormality.

Exclusions for Analysis Purposes

Invalid registry reports and pregnancies deemed lost to follow-up will be excluded from the primary analysis. Retrospective reports will not be included, although retrospective

cases with MCMs will be reviewed and reported separately for signal detection purposes. In the event that it cannot be ascertained to which meningococcal B vaccine the woman was exposed, an unknown exposure cohort will be established and analyzed separately.

Sequential Pregnancies

The number and outcome of sequential pregnancies will be noted and presented. Sequential pregnancies will be included in the analytic dataset.

Multiple Gestation Pregnancies

The number, type (e.g., twin, triplet), and outcome of multiple gestation pregnancies will be noted and presented. Multiple gestation pregnancies will be included in the analytic dataset.

General Considerations for Data Analyses

This study is observational, and epidemiological methods will be employed for data collection and analyses.

Descriptive analysis will be performed for all prospective, evaluable data. The summary statistics for continuous and categorical variables to be used will be specified in the statistical analysis plan (SAP) but may include means, standard deviations, medians, minimums, maximums, percentiles, frequencies, and percentages. For analyses of associations between pregnancy outcomes and BEXSERO exposure, confounding and effect modification will be evaluated descriptively.

The registry will identify the number of cases for the primary outcomes of MCM, preterm birth, LBW, and in addition for second trimester SABs; prevalence estimates will be calculated as proportions of these outcomes from the total number of pregnant women or live births, or in the case of second trimester SABs, the subset of women exposed prior to the 20th week of gestation. For each prevalence estimate, both 1-sided and 2-sided 95% confidence intervals will be calculated and reported. One-sided confidence intervals are appropriate as we are specifically interested in detecting outcome prevalence estimates greater than their respective reference prevalence, and 2-sided confidence intervals will provide further description of the accuracy of the estimates.

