6. MILESTONES

Table 6-1 Overview of study milestones.

Milestone	Planned date
Start of data collection	31 January 2016
End of data collection	The pregnancy registry will continue enrolling exposed pregnancies for a period of 3 years (final enrollment: 31 January 2019) and subsequent follow-up of enrolled infants will continue until 30 November 2019 (maximum 10 months follow-up post enrolment) or pending CBER review and discussion of results with GSK.
Annual updates	Annual interim reports will be provided to CBER per the PMC.
Final report of study results	A final report will be produced approximately 6 months after all data have been collected and cleaned and will be submitted to CBER by 31 May 2020.

Abbreviations: CBER = Center for Biologics Evaluation and Review; IRB = institutional review board; GSK = GlaxoSmithKline Biologicals S.A.

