- Tobacco, alcohol, and illicit drug use during pregnancy

Pregnancy Follow-up

Around the end of the second trimester and in the month of the EDD, the ***Interim Pregnancy Follow-up Form*** and ***Pregnancy Outcome Form***, respectively, will be requested from the obstetric HCP.

Information Collected at Interim Pregnancy Follow-up and Pregnancy Outcome

Interim Pregnancy Follow-up at End of Second Trimester

Pregnancy Status

- Updates to EDD (i.e., CEDD)
- Subsequent prenatal tests (diagnostic or screening) performed and findings including the identification of congenital anomalies
- Pregnancy complications (preterm labor, eclampsia, placental abruption)
- Details of pregnancy outcome if pregnancy is not ongoing as described below

Other Exposures

- Concomitant medications and vaccinations
- Tobacco, alcohol, and illicit drug use during pregnancy

Additional Information Collected at Pregnancy Outcome

Fetal Outcome

- Pregnancy outcome (live birth, stillbirth, SAB, IAB, ectopic pregnancy, molar pregnancy)
- Date of outcome of pregnancy
- Gestational age at outcome
- Fetal/infant characteristics: sex, birth weight
 - MCM(s) and assessment of potential contributing factors
 - For a fetal loss (SAB, stillbirth), factors that may have had an impact on the fetal loss and attribution

Targeted Follow-up Process

If there is an MCM or other event of interest noted, in order to properly characterize the event, additional information may be requested from the reporting HCP on the **Targeted Follow-up Form**:

- Details of the MCM/condition
- Etiology
- Outcome attribution
- Specific questions requested by GSK and/or the MCM evaluator

Attempts to Obtain the Follow-up Information

In the month that the follow-up is due, the HCP will be contacted and asked to provide follow-up information. Three subsequent attempts, as necessary, will be made every 2 weeks via various modes of communication. If there is still no response from the provider, a final communication will be sent indicating the case is lost to follow-up. If this communication prompts a response from the HCP or the requested data is later received, the case will be re-opened and assessed for evaluability. If, at any point in the follow-up process, the reporter indicates that the patient is lost to follow-up, no further attempts will be made.

Follow-up Process for Clarification of Information

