9.4.4 Advisory Committee(s)

An SAC will be established to oversee the scientific affairs of the registry, including its ongoing monitoring. The SAC will comprise recognized experts in the fields of teratology, epidemiology, maternal and fetal medicine, and therapeutic areas from government, academia, private practice, and GSK. The SAC will meet prior to each registry report to review the accumulated body of data from the registry, including review and classification of reported MCMs, and to carry out any actions required, including review and interpretation of interim data analyses and reports and publications of registry data. The SAC may meet on ad hoc occasions if indicated. In addition to the above activities, the SAC will design and implement strategies to heighten awareness of the registry.

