9.7.4 Statistical Considerations

Because early prenatal testing is so frequent, it may be difficult to achieve adequate numbers of prospectively identified pregnant women if all pregnancies with prior prenatal testing are excluded from the analysis. Therefore, the primary analysis will include pregnancies enrolled prior to outcome but after prenatal test as long as the test does not indicate an abnormality. However, this practice could potentially bias the results by lowering the overall risk of MCMs (Honein, 1999). The analysis will attempt to determine bias introduced by this practice by examining the data with and without these cases.

While the registry analysis will be limited primarily to prospective reports, some pregnancy exposures will be reported only following pregnancy outcome (retrospective cases). Each retrospective report will be carefully reviewed. In general, retrospective reports of exposures to vaccines or medication following notification of outcome are biased toward reporting of the severe and unusual cases and are not reflective of the general experience with the vaccine or medication. Moreover, information about the total number of exposed persons is not known. Therefore, prevalence estimates of outcomes cannot be calculated from these data. However, a series of reported MCMs can be analyzed to detect patterns of specific MCMs and can identify early signals of vaccine or medication risks.

Those pregnancies that have reached EDD, but for which outcome information was unobtainable after 4 attempts, will be considered lost to follow-up. It is possible that outcomes among pregnancies lost to follow-up could differ from those with documented outcomes. Because of differences in individual reporting patterns, it is currently not possible to assess with any certainty what impact the potential biases the losses to follow-up may have on the analysis. However, efforts at comparing some of the characteristics of

each group may be conducted in an attempt to assess this potential source of bias (details to follow in the SAP).

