11. MANAGEMENT AND REPORTING OF ADVERSE EVENTS/ ADVERSE REACTIONS

The registry will follow industry guidance (FDA, 2002) for regulatory reporting of adverse events (AEs), as stated below:

“The Agency considers pregnancy exposure registry reports (both prospective and retrospective) as derived from active solicitation of patient information. Accordingly, a sponsor holding marketing authorization for an approved drug or licensed biological product must submit to the Agency, within 15 calendar days, reports of adverse events from the registry that are both *serious* and *unexpected* by regulatory definition and where a reasonable possibility exists that the drug or biological product caused the adverse event [see 21 CFR 310.305(c)(1), 314.80(c)(2)(iii) and (e), and 600.80(c)(1), (c)(2)(iii) and (e)]. Current reporting requirements in the regulations consider any congenital anomaly within the definition of a serious adverse event [21 CFR 314.80(a) and 600.80(a)].” (FDA, 2002)

In addition to the above, because the registry is a study specifically to follow-up in pregnant women, exposure in pregnancy to the vaccine of interest itself will not be reported individually but will be reported by PPD to the sponsor’s Safety Department on a monthly basis as line listings. The registry final report will summarize the data on these exposures in pregnancy reported to the registry. Additionally, annual CBER PMC updates, periodic safety update reports (PSURs), and development safety update reports (DSURs) will provide data on exposure in pregnancy reported to the registry. For subjects enrolled in the registry, exposure in pregnancy to any other product (as well as the vaccine of interest) for which the sponsor is the market authorisation holder (MAH) will be collected and reported on the monthly line listing. For subjects not enrolled in the registry, exposure to any product for which the sponsor is the MAH will be reported within 1 business day to the sponsor’s safety department as an individual report.

The registry will limit active solicitation of AEs to specific pregnancy outcomes and they will be classified as serious adverse events (SAEs). These actively solicited SAEs include MCM, LBW, preterm birth, SAB, still birth, IAB, molar pregnancy, and ectopic pregnancy. In addition to actively solicited SAEs, any maternal death will be reported as individual case safety reports (ICSRs) to the sponsor’s safety department.

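### Annual interim preterm-birth and low-birth-weight estimates count any known outcome without requiring that the due date has passed, which biases them modestly upward while enrollment is open

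*Combined protocol and SAP*

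**What the plan says.** - **Inclusion.** Section 9.7 (Evaluable Registry Reports): "Prospectively reported evaluable subjects with known outcomes will be included in the primary analysis for the registry report". The Analysis Population paragraph of the same section asks only for "participants with appropriate outcome information that meet the minimum criteria for evaluation". Neither mentions the EDD.
- **Where the EDD enters case disposition.** Section 9.7.4 uses it to declare loss to follow-up: "Those pregnancies that have reached EDD, but for which outcome information was unobtainable after 4 attempts, will be considered lost to follow-up". An ongoing pregnancy is therefore neither counted nor lost.
- **Interim use.** Section 6: "Annual interim reports will be provided to CBER per the PMC". Section 9.4.4: "The SAC will meet prior to each registry report to review the accumulated body of data from the registry", including "review and interpretation of interim data analyses". Enrollment runs from 31 January 2016 to 31 January 2019, so annual cuts fall within it.
- **Estimates.** Section 9.7.3 defines preterm-birth and LBW prevalence as live births with the outcome divided by all live births. They are compared with national vital statistics, and 1-sided limits are meant to detect an excess.
- **When outcomes are requested.** Section 9.4 asks for the outcome form in the month of the EDD. The form at about 24 weeks also takes "Details of pregnancy outcome if pregnancy is not ongoing as described below".
- **Bias discussion.** Sections 9.7.4 and 9.9 discuss prenatal testing, loss to follow-up, enrollment route and random variation, but not incomplete follow-up at an interim cut.

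**The concern.** Two women enroll on the same day at the same gestational age. One delivers at 34 weeks, the other at 39. For about five weeks of calendar time the first can be in the report and the second cannot. Across a cohort that is still enrolling, each birth is weighted by the calendar window in which enrollment could already have led to a known outcome, and that window is longer for shorter pregnancies. Preterm birth is defined by short gestation, so its share of completed live births rises with no vaccine effect. LBW follows in part, because many LBW infants are preterm.

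The national reference comes from complete birth cohorts, so the interim comparison is not like with like. The error also points toward the excess that the 1-sided interval is meant to find. At stake is the accuracy of the interim estimates seen by the Scientific Advisory Committee (SAC) and CBER, above all the first.

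**Working it through.** **1. The plan's own figure.** Section 9.5 gives a detectable ratio of 1.79 for preterm birth with 100 live births (reference 11.71%, 1-sided 5%, 80% power). By exact binomial, the smallest r with P(X ≥ r | 100, 0.1171) ≤ 0.05 is 18 (actual alpha 0.042). Solving P(X ≥ 18 | 100, p) = 0.80 gives p/0.1171 = 1.789. All 15 cells of Table 9.5-1 reproduce to within 0.005, so the same test is used in step 7.

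**2. Inputs.** From the documents: preterm 11.71%, LBW 8.50%, cuts at 52, 104 and 156 weeks, and 5-150 live births considered. Assumed, because the documents do not give them: true prevalences equal to the references, uniform accrual, enrollment at gestational age e = 6-20 weeks, mean gestation 34.39 weeks (preterm) and 39.42 weeks (term), and 67% of LBW infants preterm.

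**3. Outcome known at delivery.** A birth at gestation g is counted at week T if the woman enrolled before T − (g − e). For T = 52 and e = 10:
- preterm window: 52 − 24.39 = 27.61 weeks
- term window: 52 − 29.42 = 22.58 weeks
- average: 0.1171 × 27.61 + 0.8829 × 22.58 = 23.17 weeks
- apparent preterm prevalence: 0.1171 × 27.61 / 23.17 = 13.95%, ratio 1.19
- LBW: window 0.67 × 27.61 + 0.33 × 22.58 = 25.95; 8.50% × 25.95 / 23.17 = 9.52%, ratio 1.12

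**4. Outcome learned through the EDD-month request.** This is taken as 38 weeks or delivery, whichever is later. For T = 52 and e = 10 the preterm window is 52 − 28 = 24.0 and the average is 22.7, so prevalence is 0.1171 × 24.0 / 22.7 = 12.38%, ratio 1.06.

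**5. Preterm ratios over e = 6-20 weeks, uniform accrual.**

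| Cut | Learned from the EDD-month request | Known at delivery |
|---|---|---|
| Year 1 | 1.04-1.07 | 1.13-1.23 |
| Year 2 | about 1.02 | 1.05-1.06 |
| Year 3 | 1.01 | 1.03-1.04 |

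If accrual rises linearly, the year-1 ratios become 1.08-1.14 and 1.29-1.52, and the year-3 ratios about 1.02 and 1.07.

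**6. Births available at year 1.** With 150 in total over 156 weeks: 150 × 19.2/156 = 18 (e = 6), 150 × 23.2/156 = 22 (e = 10), 150 × 33.2/156 = 32 (e = 20). The standard error at 22 births is √(0.1171 × 0.8829 / 22) = 6.9 percentage points. The bias at e = 10 is 12.38 − 11.71 = 0.7 or 13.95 − 11.71 = 2.2 points.

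**7. False-signal rate at N = 22.** The exact cut-off is r = 6. P(X ≥ 6) is 3.7% at 11.71%, 4.6% at 12.38% and 7.6% at 13.95%.

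**8. Final report.** From 31 January to 30 November 2019 is 303 days, or 43.3 weeks after last enrollment. Essentially every pregnancy has ended, so the bias vanishes.

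**9. With a due-date rule.** Counting only pregnancies past EDD + 2 weeks (42 weeks) gives every birth the same window, 52 − 32 = 20.0 weeks at e = 10. The estimates return 11.71% and 8.50% at every cut.

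**The case against.** The strongest defence is the follow-up schedule. The outcome form is requested in the EDD month, so most preterm births may not be known much before term births. This stands as a limit on size: it lowers the year-1 ratio to 1.04-1.07. It does not bring the ratio to 1, because some later deliveries are still pending, and nothing in Section 9.7 bars counting an outcome reported sooner.

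Several stronger readings are tempting but not supported:

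- **That the safety rules force adverse outcomes in early.** Section 11 says "These actively solicited SAEs include MCM, LBW, preterm birth, SAB, still birth, IAB, molar pregnancy, and ectopic pregnancy". This classifies outcomes. The one-business-day clock in that section starts when the registry's contractor becomes aware, and no provider is required to report at delivery.
- **That the 24-week form drives the bias.** Pregnancies over by then are mostly losses, which are in neither numerator nor denominator of the two proportions.
- **That false signals would be frequent.** At 50 births and a prevalence of 14.0% the rate would be 8.2% rather than 2.8%. But 50 births at year 1 (e = 10) implies 50 × 156/23.2 = 336 in total, against a planned maximum of 150.
- **That stopping decisions would be distorted.** The Section 13 criteria concern sample size, feasibility and better data sources. None uses an observed preterm or LBW excess. The formal signal rule in Section 9.4.5 concerns malformations.

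It is also fair that the registry is described as primarily descriptive, and that Sections 9.7.2 to 9.7.4 defer details to an SAP. No data-cut rule appears in the text supplied, but one in a separate SAP cannot be excluded.

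**Conclusion.** The point holds for the annual interim estimates of preterm birth and, less strongly, LBW. The inclusion rule as written over-represents short gestations whenever enrollment is open at the cut. The direction is certain under that rule. The size is modest and rests on the assumptions in step 2, chiefly when outcomes become known and how accrual runs. Under uniform accrual, year-1 preterm prevalence is inflated by about 4-7% (EDD-month learning) to 13-23% (known at delivery), falling to about 1-4% by year 3. Rising accrual would make it larger.

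A reader might infer a built-in false safety signal or a flawed study result. Neither follows. At the births expected at year 1, sampling error exceeds the bias, and under EDD-month learning with 22 births the false-signal rate stays below the nominal 5%. The final analysis is essentially unaffected. The harm is a modestly misleading interim safety estimate reviewed by the SAC and CBER. Late enrollment can bias preterm prevalence downward by left truncation; that is a separate matter and was not modelled.

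**What to change.** Add to Section 9.7: interim preterm-birth and LBW prevalence estimates include only pregnancies whose EDD plus a stated follow-up contact window had passed at the data cut, whatever the date on which the outcome became known. Outcomes of other pregnancies are listed case by case, so signal review loses nothing.

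The cost is a date filter and smaller interim denominators. With a 2-week window and e = 10, the loss relative to counting at delivery is 1 − 20.0/23.2 = 14% of live births at year 1, 1 − 72.0/75.2 = 4% at year 2 and 1 − 124.0/127.2 = 3% at year 3. The window length should be chosen deliberately. Section 9.4 allows three further attempts at 2-week intervals. A 6-week window would leave 52 − (46 − 10) = 16.0 weeks at year 1, a loss of 1 − 16.0/23.2 = 31%. The final analysis is unchanged.
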